- 2) Recruitment of 60 individuals who live in Winnipeg, MB to wear an accelerometer. We will employ a convenience sampling approach, where participants who are already using the App and participating in the study (i.e., the 300 participants described above) will be asked to participate if they live in Winnipeg. Additionally, we will employ a convenience sampling approach at the St. Boniface Hospital, University of Manitoba, and Tactica Interactive. Participants will be contacted via e-mail. First, we will use an e-mail approach to contact participants. The e-mail approach will provide contact information for potential participants to reach research staff to facilitate the recruitment and consent of participants at a mutually agreeable location. Secondly, we will use a poster advertisement approach (**Appendix 7**) to facilitate recruitment. Posters will be placed around the St. Boniface Hospital, University of Manitoba, and Tactica Interactive. In total for the sub-study, more than 12,000 staff members at the St. Boniface Hospital, 8,700 faculty/staff, at the University of Manitoba, and Tactica Interactive will be accessible, including:
 - Nurses and Nurse Practitioners;
 - Physicians;
 - Property Management (electrical, carpentry, mechanical);
 - Administrators and clerical support staff; and,
 - Researchers
 - Software developers

Study procedures

Large study procedures:

After participants choose to participate in the study, participants will be asked to complete a series of questionnaires at baseline, one week and every month for a total of six months (i.e., 8 different

occasions). The questionnaires (**Appendix 8**) will take approximately 30-45 minutes to complete and comprise of the following:

- 1) Demographics
- 2) Depressive symptoms with the Patient Health Questionnaire-9
- 3) Physical activity using the Godin Leisure Time Exercise Questionnaire
- 4) Cardiovascular health risk using the Cardiovascular Health in Ambulatory Care Research Team (CANHEART) questionnaire
- 5) Occupational Sitting with the Occupational Sitting and Physical Activity Questionnaire
- 6) Self-efficacy levels for physical activity and reducing sedentary time with the Exercise Self-Efficacy Questionnaires and Self-Regulatory Efficacy to Manage Sedentary Behavior questionnaire
- 7) Confidence levels for reducing sedentary behaviors with the Barrier Self-Efficacy to Reduce Sedentary Behavior and Self-efficacy to Reduce Total Daily Sedentary Time questionnaires.

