- 8) Physical activity levels at the workplace with the Workplace Sitting Breaks Questionnaire

Research participants will be prompted within the App to a hyperlink to complete the research questionnaires on Survey Monkey. In order to track individual research participant responses The links are as follows:

- 1) Description of the study/eligibility form, consent to participate, and baseline questionnaire: <https://www.surveymonkey.com/r/L3KDHRQ>
- 2) 1 week survey: <https://www.surveymonkey.com/r/L39CZB5>
- 3) 1 month survey: <https://www.surveymonkey.com/r/L3J2M67>
- 4) 2 month survey: <https://www.surveymonkey.com/r/L3SKXGH>
- 5) 3 month survey: <https://www.surveymonkey.com/r/L3MDLCF>
- 6) 4 month survey: <https://www.surveymonkey.com/r/L3FLMWG>
- 7) 5 month survey: <https://www.surveymonkey.com/r/L3B28KX>
- 8) 6 month survey: <https://www.surveymonkey.com/r/L3P9FGC>

[figure not shown]
Participants will also be asked on two separate occasions over the 6 month period to document their experiences using an experience sampling approach. A list of questions used are in **Appendix 5**.

Sub-study procedures:

Participants from Winnipeg, MB who choose to enroll in the sub-study will complete the study procedures for the large study and will also be asked to meet with research staff to obtain consent for the smaller study and will be asked to wear an accelerometer for 7-day periods at baseline and every month for 6 months (i.e., 7 different occasions). The research appointments will last approximately 30 minutes each.

See below for a figure overviewing the flow of the study.

Figure 1. Study flow chart

Assessment of Safety

Since this is not a drug study, rescue medication is not warranted. Should any participant experience adverse effects as a consequence of participation in the study, they will be excluded from the study and receive routine clinical care. All serious adverse events as well as death due to any cause or cardiovascular death will be reviewed by the medical monitor within 24 hrs of becoming aware of events. Any Serious Adverse Events will be reported to the University of Manitoba Health Ethics Boards and St. Boniface Hospital.

Statistics

Sample Size

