The primary outcome for this time series quasi-experimental study is a change in moderate-vigorous physical activity within the subset of 60 participants. When doing a pre/post power analysis, an estimate of correlation between the pre and post measurements is required. We assumed a high correlation of 0.8 between measurements. Under this assumption, the sample size needed to detect a 20 minute/week increase for moderate-vigorous physical activity (Mean \pm SD; Pre: 72 \pm 64 min/week; Post: 92 \pm 86 min/week) is n=44 for with a two tailed α of 0.05 and power of 80%. Even so, we will recruit 60 participants to account for the possibility of drop out. If we assume a moderate correlation of 0.5 between Pre-Post, the sample size of 60 will still be large enough to detect a change in total physical activity (Pre: 1240 \pm 182 min/week; Post: 1402 \pm 455 min/week).

Study Data

For the experience sampling and Flurry Analytics approach to this study, data from participants at the aggregate level using the mobile App will be analyzed to categorize responses, generate frequency charts, and define themes

For the quasi-experimental design, a one-way repeated measures ANOVA or Mann-Whitney Test will be used to examine changes in breaks in sedentary time and other continuous outcome measures from baseline to 1 week, 1-month, 2-month, 3-month, 4-month, 5-month, and 6-month depending if the data are normally distributed. Categorical variables will be compared using a Chi-Square test. Relationships between variables will be assessed using Pearson or Spearman correlations, as well as multivariable linear or logistic regression.

Informed consent

The written consent form will be reviewed by the Health Research Ethics Board at the University of Manitoba prior to the initiation of the study. The consent form will describe the study procedures, risks and possible benefits, and will be reviewed by the participant prior to their enrollment in the study. Each participant will be asked to read the consent form and will be provided an opportunity to ask questions before they are enrolled. All participants will be required to provide written consent prior to initiation of study procedures. The consent form will be signed and dated by the participant and will be counter-signed by the researcher who conducted the informed consent process. The researcher will retain the original signed consent form and a copy of the form will be provided to the participant.

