ENCOURAGE APP – statistical analysis plan:

For the primary outcome, a one-way repeated measures ANOVA or Mann-Whitney Test will be used to examine changes in the number of breaks in sedentary time from baseline to 1-month, depending if the data are normally distributed.

Other secondary, continuous outcome measures will be analyzed with a one-way repeated measures ANOVA or Mann-Whitney Test from baseline to 1 week, 1-month, 2-month, 3-month, 4-month, 5-month, and 6-month depending if the data are normally distributed. Categorical variables will be compared using a Chi-Square test. Relationships between variables will be assessed using Pearson or Spearman correlations, as well as multivariable linear or logistic regression.

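### For non-normal data the plan names the Mann-Whitney test, which assumes independent samples, for changes within the same participants; at n=60 this costs most of the power of a paired test

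*SAP*

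**What the plan says.** The SAP has two sentences on continuous outcomes. The first covers its primary outcome, "changes in the number of breaks in sedentary time from baseline to 1-month". The second reads "Other secondary, continuous outcome measures will be analyzed with a one-way repeated measures ANOVA or Mann-Whitney Test from baseline to 1 week", then lists months 1 to 6. Both choose between a repeated-measures ANOVA and Mann-Whitney according to normality. The protocol (Statistics, Study Data) makes the same choice for sedentary breaks and for "other continuous outcome measures from baseline to 1 week, 1-month, 2-month, 3-month, 4-month, 5-month, and 6-month". Neither document names a paired or repeated-measures rank test.

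The protocol's Sample Size paragraph says that for a pre/post calculation "an estimate of correlation between the pre and post measurements is required". It assumes 0.8 for moderate-vigorous activity (MVPA), and for total activity it says "If we assume a moderate correlation of 0.5 between Pre-Post, the sample size of 60 will still be large enough to detect" the change. On attrition it says only "Even so, we will recruit 60 participants to account for the possibility of drop out".

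On timing, the large study gives "questionnaires at baseline, one week and every month for a total of six months", which is 8 occasions. The sub-study is to "wear an accelerometer for 7-day periods at baseline and every month for 6 months (i.e., 7 different occasions"), with no 1-week wear.

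**The concern.** Mann-Whitney compares two separate groups. Here there is no second group: each participant supplies both the baseline value and the follow-up value. The test therefore treats variation between people as noise, although it cancels when each person is compared with their own baseline.

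The fallback is not remote. MVPA cannot be negative, and the protocol's baseline SD is 64/72 = 0.89 of the mean, which suggests skew. If the normality check fails, the analysis drops the pairing on which the sample size was built, and a real change in the sub-sample could easily be missed.

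A lesser matter is that the repeated-measures ANOVA is under-described. The SAP uses one label for a two-occasion comparison and for the full list of visits, and no missing-data rule is given.

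**Working it through.** **Inputs** (Protocol, Sample Size): MVPA 72 (SD 64) before and 92 (SD 86) after, so a change of 20 min/week; correlation 0.8 or 0.5; two-sided 5%; n=60. Total activity 1240 (SD 182) and 1402 (SD 455). Cohort of 300 (Trial design).

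**1. The plan's own figure.** SD of the change at r=0.8 = √(64² + 86² − 2×0.8×64×86) = √2685.6 = 51.8. Paired n = (1.96 + 0.842)² × 2685.6/20² = 52.7, so 53 (55 with the t distribution). The stated 44 does not follow from these inputs. Averaging the two SDs to 75 gives 44.15. That mismatch is a separate matter. What counts here is that a figure of this order needs the pairing: an independent-samples calculation gives 2 × (1.96 + 0.842)² × 5746/400 ≈ 226 per occasion, where 5746 = (64² + 86²)/2.

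**2. Hand check of the loss (normal approximation).** Treating occasions as independent uses a standard error of √(11492/60) = 13.84 (11492 = 64² + 86²), so the observed change must exceed 1.96 × 13.84 = 27.1 min/week.
- r=0.8: true standard error 51.8/√60 = 6.69. Power = P(Z > (27.1 − 20)/6.69 = 1.07) ≈ 14%.
- r=0.5: SD of change √(11492 − 5504) = 77.4, standard error 9.99. Power = P(Z > 0.71) ≈ 24%.

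With the pairing kept, a paired t-test has 84% and 50%. Simulated Mann-Whitney on normal data gives 16% and 25%.

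**3. Skewed data**, the case in which the fallback applies. Lognormal shape (assumed) matched to the means and SDs, n=60, 8,000 simulations. Each pair of figures sets the correlation on the log scale / on the raw scale.

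| MVPA | Mann-Whitney | Signed-rank |
|---|---|---|
| r=0.5 | 27% / 26% | 55% / 61% |
| r=0.8 | 19% / 17% | 90% / 95% |

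Repeat runs agree within simulation error, with Mann-Whitney up to 28%. With identical distributions at both occasions, Mann-Whitney rejects in 0.8% (r=0.5) and under 0.1% (r=0.8) of trials; signed-rank stays near 5%.

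**4. The cohort of 300.** With the same MVPA effect, Mann-Whitney reaches about 98% (r=0.5) and over 99% (r=0.8). At n=240 it has 94% and 99%. For an assumed smaller change, 72 to 80 with the SD rising in proportion (64 to 80×64/72 = 71), it has about 27–33% against 60–94% for signed-rank. The gap narrows if the SD stays at 64.

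**5. When spread changes.** For MVPA the SD rises nearly in proportion to the mean (64/72 = 0.89; 86/92 = 0.93). For total activity it does not (182/1240 = 0.15; 455/1402 = 0.32). With equal means and SDs of 182 and 455 (n=60, lognormal), rejection rates are:
- Mann-Whitney: about 11–16% (r=0.5) and 7–11% (r=0.8), depending on the common mean chosen.
- Signed-rank: about 10–13%.
- Paired t on logs: about 26% and 35%.
- Paired t on raw values: about 5%.

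So in this case neither rank test nor the log-scale test targets the mean change. At the planned total-activity change and r=0.5, power is 42–43% for Mann-Whitney, 78–79% for signed-rank and about 91% for the raw paired t.

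**6. ANOVA reading.** Complete cases in one classical model are 300(1−p)⁷ for questionnaires and 60(1−p)⁶ for accelerometer outcomes, where p is an assumed independent miss rate per follow-up.

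| p | One model, of 300 | Pairs at month 6 | One model, of 60 | Pairs at month 6 |
|---|---|---|---|---|
| 5% | 210 | 285 | 44 | 57 |
| 10% | 143 | 270 | 32 | 54 |
| 20% | 63 | 240 | 16 | 48 |

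Against a mixed model, available pairs give a standard error of the 6-month change only 0.4–4.5% larger (questionnaires) or 0.3–3.6% larger (accelerometer), for miss rates of 2–20%.

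**The case against.** The best defence is about impact, and much of it stands.

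- **Most secondary outcomes are questionnaires in 300 people.** There an effect of the MVPA size is found even with the wrong test. A reader might infer that real changes in skewed outcomes would generally be missed. The documents do not support that: they give no effect size for any questionnaire outcome, so only smaller effects are at risk.
- **A reader might infer that Mann-Whitney is always too conservative here.** That holds only when the distribution does not change. With the total-activity SDs and equal means it rejects more often than 5%, and so does signed-rank. Simply substituting signed-rank is therefore not a full remedy.
- **The test applies only if normality fails.** The low power figures are not the power of the trial as planned, since the ANOVA branch respects the pairing.
- **A reader might infer that the ANOVA will discard everyone who misses a visit.** The text does not settle this. Separate baseline-to-visit comparisons are an equally open reading, and the large losses in step 6 need the one-model reading, complete-case software defaults and assumed miss rates together. The protocol speaks only of possible drop-out.

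The defence leaves the main point untouched. Mann-Whitney is a specific test, named in both documents, and nothing elsewhere in them makes the two occasions independent.

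**Conclusion.** The fallback is wrong as written, for both the primary and the secondary outcomes in the SAP and for the matching sentence in the protocol. In the 60-person sub-sample, with the protocol's MVPA figures, it leaves about 17–28% power where a paired rank test has about 55–95%. This rests on the protocol's means, SDs and correlations and an assumed lognormal shape; normal data give the same pattern. The MVPA figures illustrate the loss. They do not measure it for the SAP's primary outcome, sedentary breaks at 1 month, for which no effect size is given. That the protocol names MVPA as primary is a separate conflict to reconcile.

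The ANOVA structure and missing-data rule are missing detail rather than error, and their effect cannot be sized from the documents. The 1-week entry is clerical for accelerometer outcomes, which have 7 occasions rather than 8. The point should be corrected before analysis; it does not call the design into question.

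**What to change.** In both SAP sentences and in the protocol's Study Data paragraph, replace Mann-Whitney with one stated paired fallback and leave the time points as they are. Possible wording:

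> If the data are not normally distributed, the mean within-person change from baseline will be estimated from paired values with a bootstrap 95% confidence interval. A Wilcoxon signed-rank test will be reported in support; it does not test the mean change when the spread differs between occasions.

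Both branches then concern change in the mean, so the unstated normality criterion no longer decides what is estimated.

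As a secondary suggestion, state whether the repeated-measures ANOVA is one model or a set of baseline-to-visit comparisons. If it is one model, fit it as a mixed model with categorical time on all available occasions (8 for questionnaires, 7 for accelerometer), so that a participant who misses one visit is kept. The gain over complete cases depends on miss rates that the documents do not give; over available pairs it is small.

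The cost is SAP and protocol wording and a little more analysis work, with no new data. The mixed model also brings a missing-at-random assumption, which should be stated and which the data cannot verify.

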
Trial objectives and purpose

The objectives of this study are to determine if the final product ENCOURAGE App can over a 6 month period:

- 1) Enhance physical activity levels; and,
- 2) Improve cardiovascular health risk;

Trial design

The public release of the ENCOURAGE App will involve two phases (Figure 1):

- 1) The recruitment of 300 individuals through the App. Any user will be able to download the ENCOURAGE App through the iTunes Store or Google Play. Note that when participants download the App, they are not automatically enrolled in the study. Participants will be prompted, after downloading the App, with a brief description of the study, as well as a pre-screening tool will be used to determine eligibility (see below for inclusion/exclusion criteria). Users will be asked via a textbox to determine if they wish to participate in a research project. Users will be asked to participate in a *time series quasi-experimental design* study to determine if the ENCOURAGE App can support participants to increase their physical activity levels over a 6 month period. The App uses a time management technique (i.e., Pomodoro technique) as a strategy to provide prompts for users to engage in an activity. The App can be customized by the users to set prompts at intervals that fits into their schedule. For example, these activities can range from a stretching activity (e.g., a neck stretch), a standing activity (e.g., stand and read), or a physical activity (e.g., fill up the printer with paper, do a squat). Additionally, the App will use Behavior Change Techniques as a way to support participants as they reduce their sedentary behavior and improve their physical activity levels.⁷ The App uses a series of Behavior Change Techniques shown to be effective in promoting a more physically active lifestyle.^{8,9} Users will also provide feedback regarding the App using an *experience sampling approach*, which uses a list of questions to guide user feedback (**Appendix 5**). Additionally, we will use *Flurry Analytics* (<http://www.flurry.com/>) to measure, track, and analyze the ENCOURAGE App performance, and aggregate-level user activity within the App. Specifically, we wish to determine the number of user sessions within the App, frequency of use, session length, user events, technical data and errors, and user geographic distribution. For a more detailed description of the experience sampling and Flurry Analytics approaches, see **Appendix 6**.

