(e.g., fast walking, baseball, tennis, easy bicycling, volleyball, badminton, easy swimming, alpine skiing, popular and folk dancing)

TIMES PER WEEK _____

c) MILD EXERCISE (MINIMAL EFFORT) (e.g., yoga, archery, fishing from river bank, bowling, horshoes, golf, snow-mobiling, easy walking)

TIMES PER WEEK _____

2. During a typical 7-Day period (a week), in your leisure time, how often do you engage in any regular activity long enough to work up a sweat (heart beats rapidly)?

OFTEN

SOMETIMES

NEVER/RARE

1.

2.

3.

CANHEART QUESTIONNAIRE – TOBACCO USE

1. Never used tobacco: 2. Ex-tobacco user: Quit date _____ 3.

Currently use:

If tobacco user, average number per day _____ and number of years _____

CANHEART QUESTIONNAIRE – FRUIT AND VEGETABLE CONSUMPTION

The next questions are about the foods you usually eat or drink. Think about all the foods you eat, both meals and snacks, at home and away from home.

1. How often do you usually drink fruit juices such as orange, grapefruit or tomato? (for example, once a day, three times a week, twice a month)

Times/day _____ OR Times/week _____

2. Not counting juice, how often do you usually eat fruit?

Times/day _____ OR Times/week _____

3. How often do you (usually) eat green salad?

Times/day _____ OR Times/week _____

4. How often do you usually eat potatoes, not including French fries, fried potatoes, or potato chips?

Times/day _____ OR Times/week _____

5. How often do you (usually) eat carrots?

Times/day _____ OR Times/week _____

6. Not counting carrots, potatoes, or salad, how many servings of other vegetables do you usually eat?

Times/day _____ OR Times/week _____

CANHEART QUESTIONNAIRE – HIGH BLOOD PRESSURE

1. We're interested in conditions diagnosed by a healthcare professional. Do you have high blood pressure? (please circle one)

Yes No

2. If yes, how old were you when you were first diagnosed?

Age in years _____

CANHEART QUESTIONNAIRE - DIABETES

1. We're interested in conditions diagnosed by a healthcare professional. Do you have diabetes? (please circle one)

Yes No

2. If yes, how old were you when you were first diagnosed?

Age in years _____

EXERCISE SELF-EFFICACY QUESTIONNAIRES**PHYSICAL ACTIVITY TASK SELF-EFFICACY QUESTIONNAIRE**

How certain are you that you can engage in moderate- to strenuous-intensity physical activity for the following durations? Please rate your degree of confidence for each duration using the scales.

10 minutes

0	1	2	3	4	5	6	7	8	9	10

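### The plan names only a Chi-Square test for categorical outcomes measured repeatedly in one group; used for change over time it is unpaired and conservative, severely so for stable items such as tobacco use

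*SAP*

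**What the plan says.** The SAP (second paragraph) and the Protocol (Statistics, Study Data) each cover all categorical outcomes in one sentence: "Categorical variables will be compared using a Chi-Square test". Neither adds which visits or which groups are compared. The sentence before it, on continuous outcomes, does list the visits.

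The design has one group and no comparator. Under Large study procedures, "participants will be asked to complete a series of questionnaires at baseline, one week and every month for a total of six months", which the Protocol counts as 8 occasions. The planned size is 300 for the questionnaire study (Trial design: "The recruitment of 300 individuals through the App") and 60 for the accelerometer sub-sample.

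Objective 2 is cardiovascular health risk, measured with the CANHEART questionnaire. Appendix 8 lists four parts:
- tobacco: never, ex or current user;
- fruit and vegetables: frequencies;
- high blood pressure: "Do you have high blood pressure? (please circle one", yes or no;
- diabetes: yes or no.

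The Godin form in the same appendix has one three-level item, on how often activity is long enough to work up a sweat.

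No paired or clustered method for categorical data is named anywhere. Logistic regression appears only for relationships between variables.

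**The concern.** With one group, the objectives can be answered only by comparing people with themselves over the 6 months. An ordinary Chi-Square on a visit-by-response table treats the baseline answers and the later answers as coming from different people. Most people give the same answer to a status question twice. The test does not use that stability, so its standard error for the change is too large.

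At stake is a false report of no change on a secondary outcome that bears on Objective 2. Tobacco use is the item where this could matter in practice. The p-values would also not have their nominal meaning.

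**Working it through.** **No figure to reproduce.** The documents give no sample size, power, rate or correlation for any categorical outcome. The only error rate and power stated ("two tailed α of 0.05 and power of 80" percent) belong to the sample-size paragraph for moderate-vigorous activity. The 5% level below is borrowed from there; every prevalence, transition rate and correlation is an assumption.

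**Step 1. Size of the standard-error mistake.** Take n people, the same proportion p at both visits, and within-person correlation φ.
- Variance of the change, paired: 2p(1−p)(1−φ)/n.
- Variance that Chi-Square uses: 2p(1−p)/n.
- So the Chi-Square z equals the correct z multiplied by √(1−φ).

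True type I error at nominal 5%: 2[1 − Φ(1.96/√(1−φ))]. At φ = 0.5: 1.96/0.707 = 2.77, giving 0.0056.

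Power of Chi-Square where the paired test has 80%: Φ((1.96 + 0.84)√(1−φ) − 1.96). At φ = 0.8: 2.80 × 0.447 − 1.96 = −0.71, giving 0.24.

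| φ | True type I error | Chi-Square power (paired test 80%) |
|---|---|---|
| 0 | 5% | 80% |
| 0.3 | 1.9% | 65% |
| 0.5 | 0.56% | 51% |
| 0.8 | 0.001% | 24% |
| 0.9 | below 0.000001% | 14% |
| 0.95 | near 0 | 9% |

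**Step 2. Worked example for tobacco.** Assume 300 people with complete answers, 60 current users at baseline and 45 at 6 months.
- Chi-Square: pooled proportion 105/600 = 0.175; SE = √(0.175 × 0.825 × 2/300) = 0.0310; z = 0.05/0.0310 = 1.61; p = 0.107, whatever the pairing.
- Exact McNemar, 15 stop and 0 start: 2 × 0.5^15 = 0.00006. Here φ = (0.15 − 0.20 × 0.15)/√(0.20 × 0.80 × 0.15 × 0.85) = 0.84.
- Exact McNemar, 20 stop and 5 start: p = 0.004.
- If nobody starts, Chi-Square needs 19 of the 60 to stop before p < 0.05 (18 gives 0.0504). Exact McNemar needs 6 (2 × 0.5^6 = 0.031).

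**Step 3. Power over a range of assumptions.** Simulated paired binary data, 20,000 runs, two-sided 5%, asymptotic McNemar:

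| n | Baseline to follow-up | φ | Chi-Square | McNemar |
|---|---|---|---|---|
| 300 | 20% to 15% | 0.84 | 19% | >99% |
| 300 | 20% to 15.8% | 0.81 | 8% | 90% |
| 300 | 20% to 11.6% | 0.60 | 92% | >99% |
| 300 | 50% to 40% | 0.61 | 80% | 98% |
| 300 | 50% to 40% | 0.41 | 75% | 90% |
| 300 | 30% to 22% | 0.44 | 64% | 85% |
| 60 | 20% to 15% | 0.84 | 0.4% | 35% |
| 60 | 50% to 40% | 0.61 | 9% | 40% |

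The loss is near total in the first two rows and modest to moderate in the next four. In a sample of 60 no test does well: in the 20% to 15% row the exact McNemar has only 8% power.

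**The case against.** **The sentence may not mean an unpaired test of change.** It names no visits, so it could refer to comparisons between different people, for which Chi-Square is correct. McNemar's test is itself of chi-square type. This stands in part: the text is underspecified, not explicitly unpaired. But both documents attach repeated measures to the ANOVA and nothing similar to Chi-Square. They also name Mann-Whitney, an independent-samples test, for within-person change. An analyst who follows the wording literally would run the unpaired test, and no other method for categorical change is offered.

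**The impact on Objective 2 is limited.** A reader might infer that three of the four CANHEART parts are lost, because three are categorical. The documents do not support that. The blood pressure and diabetes items ask about a condition diagnosed by a professional and the age at first diagnosis, so little improvement could appear in 6 months under any test. There is also no scoring rule, so it is unknown whether the parts are tested one by one or combined into a score that would fall under the sentence on continuous outcomes. This stands, and leaves tobacco as the main item.

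**The sweat item is not a declared outcome.** The Godin activity score is built from the numeric first question. This stands too; the item matters only if it is analysed.

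**The error is conservative and secondary.** It does not inflate false positives. Neither the Protocol's primary outcome (moderate-vigorous activity) nor the SAP's (breaks in sedentary time) uses this test. This bears on severity, not on whether the wording should change.

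**Conclusion.** The point holds at moderate severity. For change over visits, the only categorical test named assumes independent samples in a study where the same people answer on up to 8 occasions. The result is a conservative test: true type I error about 0.6% at correlation 0.5 and near 0 at 0.8, and power of about 51%, 24% and 14% at correlations 0.5, 0.8 and 0.9 where a paired test has 80%.

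A reader might go further and conclude that real change in any categorical outcome would be almost undetectable. That is so only for very stable answers with a small net change, which is plausible for tobacco. At correlations of 0.4 to 0.6 and changes of about 8 to 10 points in 300 people, Chi-Square still had 64% to 92% power.

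The direction of the error follows from the design whenever answers are positively correlated within a person. Its size rests on assumed prevalences, transition rates and correlations, and on all 300 people giving both answers.

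**What to change.** In the Protocol (Statistics, Study Data) and the SAP, replace the Chi-Square sentence with text that does the following.

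1. States that change in categorical outcomes is compared within person, baseline versus 6 months.
2. For binary outcomes, names the exact McNemar test with the paired difference in proportions and its 95% CI. Tobacco has three levels, so define in advance its collapse to current use, yes or no.
3. If all visits are used, names logistic GEE clustered on participant, or Cochran's Q for people with complete answers.
4. If the three-level sweat item is analysed, names an ordered paired test such as the Wilcoxon signed-rank. A paired test that ignores order, such as Stuart-Maxwell, would not use the ranking of the levels.
5. Keeps Chi-Square only for comparing different people, such as completers versus drop-outs.

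It would help to say in the same place whether the CANHEART parts are analysed separately or as a score, since that decides which sentence governs them.

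Cost: wording in two documents. No new data, visits or participants are needed.
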